5.1 CURLY and participant information

Materials for the CURLY trial are largely digital, and the use of paper will be kept to a minimum. The CURLY trial is dependent on high-quality information being presented to families in a clear and efficient way. We have followed lessons learned from several NIHR trials that have recruited from the PERUKI network that effectively used and evaluated multimedia resources to improve decisionmaking about participation in trials involving children and adolescents (37). CURLY will follow a similar approach, utilising a Research Ethics Committee (REC) approved multimedia website with images and animations to offer an overview of the trial, supported by trial materials presented in an abbreviated paper format.

5.1.1 CURLY animation video

The CURLY animation is designed to provide a clear and efficient method of explaining the CURLY trial to parents/guardians and, where appropriate, children. This video will be presented prior to consent/assent, along with the accompanying Parent/Guardian Information Sheet and age-appropriate PIS (all hosted on the CURLY trial website – see Section 5.1.4).

5.1.2 CURLY eCRF and electronic consent forms

Data for CURLY will be stored on a bespoke database hosted on a secure server at the University of Birmingham, and research team members at each site will have individual accounts to enter their data. An electronic informed consent form and electronic assent form will be used. Following consent/assent, the researcher will ask questions to the parent/guardian and, where appropriate, their child, and will enter the data into the baseline electronic Case Report Form (eCRF).

5.1.3 CURLY mobile/ web app

An app for the CURLY trial will be made available to all parents/guardians participating in the trial. This will be shared at the baseline ED visit, when its use will be demonstrated. For parents/guardians who do not have a smartphone, the same features can be accessed via a web-based platform. The Carnegie Trust have identified that 99% of the UK population with school age children have access to the internet via a desktop computer, laptop, netbook or smartphone (38, 39).

The main purpose of the app is to allow parents/guardians to log cefalexin administration, in a similar way to the many commercially available products. This data will be used to monitor adherence to cefalexin treatment, particularly treatment duration, to ensure validity of the trial results. The app will assist parents/guardians to keep track of the twice daily cefalexin schedule, alongside the administration of any relevant concomitant medications (paracetamol, ibuprofen, and any other non-trial antibiotic). In addition, the app will provide a prompt to parents/guardians about the duration of the allocated cefalexin, and when their child's final antibiotic dose is due.

The app will also be used by parents/guardians to log the presence/absence of key symptoms following discharge from the ED.

5.1.4 CURLY trial website

Families will be able to access the CURLY trial website throughout the duration of the trial. This will contain information to support their participation, including copies of the trial Patient/Parent information sheets, and information reminding them how to collect a non-contaminated urine sample from their child at home.

5.2 Long-term outcomes (optional consent)

Consent will be sought from participants to allow potential future follow-up through efficient means using data available in NHS routine clinical datasets, including primary care data (e.g. Clinical Practice Research Datalink, The Health Improvement Network, QResearch) and secondary care data (Hospital Episode Statistics) through NHS England and other central UK NHS bodies. This will permit the sharing of personal identifiers (i.e. name, date of birth and NHS number) with the relevant national registry, and for the national registry to link this to their data and transfer of this information to the trial team. The consent will also allow access to other new central UK NHS databases that will appear in the future. This will allow assessment of the longer-term impact and health service usage of UTIs in children without further contact with the trial participants. Any such work will be funded and reported separately.

5.3 Sample collection (optional consent)

Consent will be sought from participants at selected sites to collect samples for futures studies into the impact of cefalexin duration on antimicrobial resistance. This is briefly described in section 24.

6. ENROLMENT, RANDOMISATION and BLINDING

6.1 Identification

Clinicians within participating EDs will be made aware of the trial. If they are providing clinical care for a patient who is potentially eligible for the study, they will briefly mention the study to the parent/guardian and, if appropriate, their child. If the child, and/or the parent/guardian are interested, they will then be introduced to a local researcher who will further explain the study to them.

6.2 Screening and enrolment

Initial study discussions with the parent/guardian and if appropriate, their child, will be undertaken by the local researcher who has been delegated this duty. However, formal assessment of study eligibility will be performed by the PI or other medically qualified member of the research team who has been delegated this task. Informed consent will then be obtained.

Non-identifiable details of all patients approached about the trial will be recorded on the online CURLY Trial Screening Log.

6.3 Randomisation

Randomisation will be provided by BCTU using a secure online system (available at https://bcturedcap.bham.ac.uk), thereby ensuring allocation concealment. Unique log-in usernames and passwords will be provided to those who have been delegated the role of randomising participants into the trial as detailed on the CURLY Delegation Log. These unique log-in details must not be shared with other staff and in no circumstances should staff at sites access the system using another person's login details. The online system will be available 24 hours a day, 7 days a week, apart from short periods of scheduled maintenance.

In the rare case of a technical failure within the online randomisation system an emergency paper back up can be used; contact the Trial Office for details.

6.4 Randomisation process

After eligibility for participation in the CURLY trial has been confirmed and informed consent has been given, the participant can be randomised into the trial using the online system. All data items on the online randomisation form must be answered prior to a participant being randomised into the trial and a Trial Number being issued.

Following randomisation, a confirmatory email will be sent to the local PI, randomiser, and the Trial Office.

The local research team should add the participant to the CURLY Trial Participant Recruitment and Identification Log which links participants with their Trial Number. PIs must maintain this document securely and it must not be submitted to the Trial Office. The CURLY Trial Participant Recruitment and Identification Log should be held in strict confidence.

6.4.1 Randomisation method

Participants will be randomised at the level of the individual in a 1:1:1:1:1 ratio to one of five cefalexin course durations (3, 5, 6, 8 or 10 days).

A minimisation algorithm will be used within the randomisation system to ensure balance in the intervention allocations over the following variables:

- Age (3 months <3 years vs 3-11 years)
- Sex (male vs female)
- Participating centre

To avoid the possibility of the intervention allocation becoming predictable, a random element will be included in the algorithm. Full details of the randomisation specification will be stored in a confidential document at BCTU.

6.5 Blinding

This is a pragmatic, open-label trial. Participants, parents/guardians and investigators will not be blinded to allocation of treatment duration and no placebo will be used. By excluding the placebo we avoid the need for every child to complete a 10-day treatment course. This is more convenient for families and will allow more accurate assessment of the potential health economic impact (e.g. with regard to nursery/school days missed and parental leave from work). It also allows investigators and clinicians to make informed decisions when assessing if additional antibiotics are needed. Informing the participant's GP

The participant's General Practitioner (GP) (family doctor) and/or community paediatrician will be notified of their patient's participation in the CURLY trial, using the CURLY GP Letter.

7. TRIAL INTERVENTION

7.1 Trial intervention and dosing schedule

All participants in CURLY will receive oral cefalexin (all cefalexin brands suitable in line with each trial site's stock).

7.1.1 Route of cefalexin administration

Cefalexin will be administered as an oral liquid suspension (to be resuspended by the site pharmacies).

7.1.2 Dose of cefalexin

CURLY will apply the British National Formulary for Children (BNFC) weight-based cefalexin dosing schedule, following the target dose of 12.5 mg/kg twice daily. Body weight should be obtained on the day of presentation to the ED by weighing children on an appropriate scale. It will be advised to weigh children in light clothes, without shoes. Body weight reported by parents is not acceptable.

To reduce the risk of dose calculation errors and ensure that the desired volume is easy to draw-up, all sites will prescribe using a study prescription chart which will include the prespecified weight-dose volume table (Table 1).

Weigh (k	mls per dose		
Lower limit	Upper limit	(twice daily)	
5	5.49	1.4	
5.5	5.99	1.5	
6	6.49	1.7	
6.5	6.99	1.8	
7	7.99	2	
8	8.99	2.3	
9	9.99	2.5	
10	11.99	3	
12	13.99	3.5	
14	15.99	4	
16	17.99	4.5	
18	19.99	5	
20	21.99	5.5	
22	23.99	6	

Weigh (k	mls per dose	
Lower limit		
24	25.99	6.5
26	27.99	7
28	29.99	7.5
30	31.99	8
32	33.99	8.5
34	35.99	9
36	37.99	9.5
38	39.99	10
40	41.99	10.5
42	43.99	11
44	45.99	11.5
46	47.99	12
48	50	12.5

Table 1: Cefalexin will be dosed according to body weight in kg by using the following dosing table:

7.1.3 Duration of cefalexin

Trial participants will be randomised to either 3 days (6 doses), 5 days (10 doses), 6 days (12 doses), 8 days (16 doses) or 10 days (20 doses) of cefalexin.

7.1.4 Cefalexin preparations

Cefalexin used for the trial will be a standard proprietary oral liquid suspension. After reconstitution, each bottle contains 100ml of suspension at a concentration of 250mg/5ml. Each patient will receive between 1 and 3 bottles, sufficient to cover their weight-based dose volume and assigned number of

treatment days/doses (Table 2). Cefalexin doses should be discussed with parents before they leave the ED.

Weight range (kg) mls per dose		Total volume (ml) needed for full course				1 bottle 2 bottles		
Lower limit	Upper limit	(twice daily)	3 days	5 days	6 days	8 days	10 days	3 bottles
5	5.49	1.4	8.4	14	16.8	22.4	28	
5.5	5.99	1.5	9	15	18	24	30	
6	6.49	1.7	10.2	17	20.4	27.2	34	
6.5	6.99	1.8	10.8	18	21.6	28.8	36	
7	7.99	2	12	20	24	32	40	
8	8.99	2.3	13.8	23	27.6	36.8	46	
9	9.99	2.5	15	25	30	40	50	
10	11.99	3	18	30	36	48	60	
12	13.99	3.5	21	35	42	56	70	
14	15.99	4	24	40	48	64	80	
16	17.99	4.5	27	45	54	72	90	
18	19.99	5	30	50	60	80	100	
20	21.99	5.5	33	55	66	88	110	
22	23.99	6	36	60	72	96	120	
24	25.99	6.5	39	65	78	104	130	
26	27.99	7	42	70	84	112	140	
28	29.99	7.5	45	75	90	120	150	
30	31.99	8	48	80	96	128	160	
32	33.99	8.5	51	85	102	136	170	
34	35.99	9	54	90	108	144	180	
36	37.99	9.5	57	95	114	152	190	
38	39.99	10	60	100	120	160	200	
40	41.99	10.5	63	105	126	168	210	
42	43.99	11	66	110	132	176	220	
44	45.99	11.5	69	115	138	184	230	
46	47.99	12	72	120	144	192	240	
48	50	12.5	75	125	150	200	250	

 Table 2: Number of bottles required for full treatment course, according to weight band and course duration.

7.1.5 Drug interaction or contraindications

For this trial, there are no drug interactions or contraindications of note for cefalexin, other than those mentioned in the licensing information. As stated in the exclusion criteria, any child with a known allergy to cefalexin or previous severe allergic reaction to any beta-lactam antibiotic will be excluded from participation in the trial.

7.2 Concomitant medication

Paracetamol and ibuprofen are commonly administered by parents/guardians to control their child's fever and associated symptoms. As per standard clinical practice, both can be administered along with cefalexin in this trial. These drugs, along with any non-trial antibiotic, will be logged on the medicine tracker page of the CURLY app and thereby captured within the eCRF.

7.3 Repeated doses

As in standard clinical practice, any doses of cefalexin that are spat out or vomited (within 10 minutes of administration) should be repeated. Considering the possibility of spillages and doses being spat/vomited, for dose regimes close to the threshold between 1 bottle/2 bottles and 2 bottles/3 bottles, supply of an additional bottle will be provided as stated on the prescription.

7.4 Premature discontinuation of cefalexin

Cefalexin may be discontinued prior to a participant completing the assigned treatment course duration. Reasons for this include:

- The baseline urine culture result demonstrates a UTI caused by a cefalexin-resistant pathogen. As per standard practice, cefalexin will be discontinued and a different antibiotic with proven pathogen susceptibility will be commenced.
- The baseline urine culture result demonstrates no growth or below threshold growth. Sites will be permitted to inform families and advise discontinuation of cefalexin therapy, should this be their standard practice.
- A significant adverse reaction to cefalexin.
- Failure to tolerate oral cefalexin treatment and/or other clinical deterioration.

All such decisions are at the discretion of the treating clinician. The reason for any premature discontinuation of cefalexin will be logged on the Change of Status and Primary Outcome Assessment eCRF by the local study team.

7.5 Extension of cefalexin course duration

After the final day of treatment, parents/guardians will be advised to obtain a medical review if they feel that their child's symptoms have not resolved. If the clinician believes the child requires additional antibiotic treatment, this will be prescribed at the clinician's discretion. Reasons for any additional non-trial antibiotics prior to the primary outcome assessment visit will be documented and logged on the Primary Outcome Assessment eCRF.

7.6 Intervention supply and storage

Standard proprietary oral liquid suspensions of cefalexin at a concentration of 250mg/5ml will be used. This will be supplied, stocked, and dispensed in line with the usual practice at each site. No clinical trial specific pharmacy requirements of the drug intervention including supply, storage, labelling, drug accountability and destruction is needed.

7.7 Adherence

In contrast to trials which investigate medications in tablet form, it will not be possible to dispense a rationed volume of liquid medication appropriate for the allocated duration arm. In paediatric practice, medication suspensions are reconstituted according to the manufacturer's instructions, and any excess volume in the bottle allows for common issues of spillage or doses being spat out by the child. The dispensing of these standard volume bottles creates a potential for non-adherence with allocated cefalexin duration, and it will therefore be necessary to monitor adherence, which will

be defined as no more than one missed dose from the allocated full course, as logged on the medicine tracker page of the CURLY app, and no additional dose(s) beyond the assigned treatment duration. The app will support adherence by providing a visual prompt to parents/guardians about the duration of the allocated cefalexin, and when their child's final antibiotic dose is due.

8. OUTCOME MEASURES

CURLY will have an internal pilot period to determine if it should continue to a full trial. The primary criteria assessed will be recruitment per centre per month. The stop/go criteria, agreed with the funder elsewhere, will be assessed after 6 months of recruitment (Table 3).

Internal pilot recruitment = 201 participants by 6 months							
Red Amber Green							
Participants recruited per centre per month	<4.5	4.5-7.49	≥7.5				
% of target recruitment per centre per month	<60%	60-99%	100				
Number of centres opened (out of 8)	<6	6-7	≥8				

Table 3: Traffic light system for progression criteria from internal pilot to main study.

8.1 Primary outcome

The primary outcome is clinical UTI cure rate, which will be assessed at a face-to-face follow-up assessment at 16 days post-randomisation. Clinical UTI cure is defined as those patients in whom there is (i) fever resolution and (ii) no additional systemic antibiotic prescription by 16 days post-randomisation. This primary outcome is informed by a systematic review that identified wide variation in the outcomes reported within paediatric febrile UTI trials, and proposed criteria to harmonise study design (32), which were endorsed by the European Medicines Agency (33).

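### Cure counts only a new antibiotic prescription, so a failure treated at home with leftover trial cefalexin can be scored as a cure, which would pull D* down by an unknown amount

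*Protocol*

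**What the plan says.** Section 8.1 (also the Trial Summary, 1.2.4 and 14.4) defines cure as fever resolution together with "ii) no additional systemic antibiotic prescription by 16 days post-randomisation".

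On supply, section 7.1.4 states that "each bottle contains 100ml of suspension at a concentration of 250mg/5ml". Section 7.7 concedes that "it will not be possible to dispense a rationed volume of liquid medication appropriate for the allocated duration arm" and that "The dispensing of these standard volume bottles creates a potential for non-adherence with allocated cefalexin duration". Section 7.3 adds that for courses close to a bottle threshold "supply of an additional bottle will be provided as stated on the prescription".

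On recording:
- Section 7.5 is titled as covering extension of the cefalexin course, but what it captures is narrower: "Reasons for any additional non-trial antibiotics prior to the primary outcome assessment visit will be documented". Sections 7.2 and 9.6 also name non-trial antibiotics only.
- The app dose log is described as running during the cefalexin course (9.1.3), and Table 4 places it at d0-d10.
- The day-16 visit asks about adherence and new prescriptions (9.1.5). It does not ask why trial cefalexin was continued.

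Extra cefalexin doses enter only the adherence outcome (7.7, 8.2.1) and, through it, the per-protocol sensitivity analysis (14.7). The main analysis is by allocated duration whatever the adherence (opening of section 14).

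**The concern.** The trial is open label (6.5), so a parent knows that the course was short and often has more of the same drug at home. Suppose symptoms persist at the end of the allocated course, the parent carries on from the bottle without review, and the fever settles by day 16. The allocated duration failed that child, yet both cure criteria are met. No section of the protocol scores this as a failure.

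The main driver of the bias is the number of failures available to reclassify. If cure rises with duration, short arms have more failures, so the same share of leftover use lifts them more. The left end of the curve rises and D* falls. For a trial meant to find the shortest effective course, that is the unsafe direction.

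**Working it through.** **1. The plan's own volumes.** Table 2 volume = ml per dose × 2 × days. For 12-13.99 kg: 3.5 × 2 × (3, 5, 6, 8, 10) = 21, 35, 42, 56, 70 ml, which matches the table row "12 13.99 3.5 21 35 42 56 70". All 27 rows reproduce.

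**2. What is left at home.** Surplus = 100 × (fewest whole bottles) − course volume. Using the fewest whole bottles is an assumption, because the table's bottle shading cannot be read in the text available. Section 7.3 can only add to it.

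| Weight band (kg) | 3 days | 5 days | 6 days | 8 days | 10 days |
|---|---|---|---|---|---|
| 12-13.99 | 79 ml | 65 | 58 | 44 | 30 |
| 18-19.99 | 70 ml | 50 | 40 | 20 | 0 |
| 20-21.99 | 67 ml | 45 | 34 | 12 | 90 |
| 48-50 | 25 ml | 75 | 50 | 0 | 50 |

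In all 12 bands below 20 kg the 10-day volume is at most 100 ml, so one bottle covers 10 days in any arm, and the surplus falls as the allocated duration rises. From 20 kg (15 bands) the pattern is not monotone, and the 3-day arm never has the largest surplus.

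**3. Effect on observed cure.** Let p be true cure and f the share of true failures treated from the bottle and then scored as cured. Observed cure = p + f(1 − p). The protocol gives neither p nor f; every value below is an assumption.

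**4. Share at which the 3-day point estimate reaches 90% of the 10-day rate.**
- Leftover use in the 3-day arm only: f = (0.9·p10 − p3)/(1 − p3).
- Equal use in all arms: f = (0.9·p10 − p3)/[(1 − p3) − 0.9(1 − p10)].

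For p3 = 0.80 and p10 = 0.95 the threshold is 0.9 × 0.95 = 0.855. This gives 0.055/0.20 = 27.5% and 0.055/(0.20 − 0.045) = 0.055/0.155 = 35.5%.

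| Assumed cure, 10 days | 3 days | f, 3-day arm only | f, all arms |
|---|---|---|---|
| 85% | 75% | 6% | 13% |
| 90% | 80% | 5% | 9% |
| 90% | 75% | 24% | 37.5% |
| 95% | 80% | 27.5% | 35.5% |
| 95% | 75% | 42% | 51% |

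**5. Effect on D\*.** Best-fitting two-term fractional polynomial (logistic), expected counts of 100 per arm, 90% rule. The protocol does not give the powers.

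| Assumed cure at 3/5/6/8/10 days | f = 0 | f = 10/20/30%, arms under 10 days | f = 10/20/30%, all arms |
|---|---|---|---|
| 70/78/82/88/90% | 5.74 | 5.20 / 4.57 / 3.82 | 5.47 / 5.13 / 4.70 |
| 75/83/86/89/90% | 4.37 | 3.87 / 3.30 / 3.00 | 4.08 / 3.75 / 3.35 |

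**6. Per-protocol analysis.** True cure 70%, f = 30%. By allocation: 0.70 + 0.30 × 0.30 = 79.0%. Per-protocol drops the 9% who extended: 0.70/0.91 = 76.9%. The bias shrinks but the 70% is not recovered, because those children are removed and not counted as failures.

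**The case against.** The path to misclassification is narrow. The app prompts when the last dose is due (5.1.3, 7.7). An alert on the final day and a check 48-72 hours after treatment direct families to medical review, and non-responders are telephoned (9.1.3, 9.5). Sites review adherence from the app data (9.1.4) and again at day 16. A child still febrile is a failure in any case. The present definition rests on an observable event, follows published harmonised criteria and had parent input (1.2.4). Scoring by parent-reported motive in an open-label trial has its own risk: parents in short arms may finish the bottle as a precaution and be counted as failures. A sensitivity analysis may also be specified in the statistical analysis plan, which is not available here.

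Much of this stands. It makes the problem less frequent and argues for caution in rewriting the primary outcome. It does not change how an affected child is scored, and no analysis plan can use a reason for extra doses that was never collected.

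Three stronger readings are tempting, but the protocol does not support them:
- *The surplus is always largest in the shortest arms.* That holds only below 20 kg. The direction of the bias rests mainly on the number of failures per arm.
- *A clinician could extend treatment from the bottle without it counting.* Section 7.5 says that extra treatment a clinician judges necessary is prescribed, and a prescription already counts as failure. What remains is continuation by the parent without review.
- *Three days would be declared adequate.* Section 14.4 recommends the smallest duration above the upper confidence limit of D*. As the shortest arm, 3 days cannot lie above the upper limit for a D* between 3 and 10 days. The bias shifts D*, and with it the recommendation, towards shorter courses.

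**Conclusion.** The gap is real. Component (ii) counts prescriptions only, the protocol itself recognises that surplus drug allows dosing beyond the allocated course, and neither the analysis by allocation nor the per-protocol analysis scores a child treated from the leftover bottle as a failure. The direction, a lower D*, depends on cure rising with duration and on leftover use in short arms being no rarer among failures than in longer arms. The size cannot be stated from the protocol. The 28% and 35% tipping shares rest on assumed cure of 80% and 95%, and they concern the 3-day point estimate, not the recommended duration. This is an inexpensive improvement to data capture and sensitivity analysis. It does not show that the result will be wrong.

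**What to change.** 1. Extend the dose log to day 16 in all arms.
2. Add one item to the day-16 eCRF: any trial cefalexin taken beyond the allocated course, and the reason.
3. Pre-specify a sensitivity analysis of D* in which any systemic antibiotic taken beyond the allocated course for persistent or recurrent symptoms, including leftover trial cefalexin, counts as not cured. Stray extra doses without symptoms remain an adherence matter.
4. The sponsor may also consider this wording for component (ii) itself.

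The cost is a longer logging period, one eCRF item and one further run of the curve. The weakness is reliance on parent report in an open-label trial: precautionary extra doses in short arms may be misread as failures and bias D* the other way. That is the reason to make it a sensitivity analysis first. No change to dispensing or treatment is proposed.
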